9.2.5. Follow-up

9.2.5.1. RZV 2-Dose Analysis

In the 2-dose analysis, the occurrence of the primary outcome, HZ, for each cohort member will be assessed from day 29 after cohort entry until the first occurrence of HZ, disenrollment from the health plan, death, end of the study period, or receipt of RZV (ie, receipt of a third dose for the RZV cohorts or a first dose for the UC comparator and RA comparator cohorts only). The start of follow-up for HZ will begin on day 29 to allow for development of an immune response following receipt of the second RZV dose.¹⁵

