9.2.5.2. RZV ≥ 1 Dose Analysis

In the ≥ 1 dose analysis, the occurrence of the primary outcome, HZ, for each cohort member will be assessed from the day after cohort entry until the first occurrence of HZ, disenrollment from the health plan, death, end of the study period, or receipt of RZV (patients in the UC comparator and RA comparator cohorts only). As patients may receive a diagnosis code for HZ on the date of RZV receipt, HZ diagnoses on the cohort entry date will not be counted as outcomes.

The occurrence of the secondary outcome, disease flare, will be assessed from the cohort entry date until the first occurrence of disease flare, disenrollment from the health plan, death, end of the study period, receipt of RZV (patients in the UC comparator and RA comparator cohorts only), or 90 days after cohort entry.

Primary and secondary outcomes will be assessed independently of one another; occurrence of the primary or secondary outcome will not lead to censoring for the other outcome. Furthermore, HZ and disease flare outcomes will be assessed in the RZV 2-Dose and Comparator 2-Dose cohorts independently of the RZV ≥ 1 Dose and Comparator ≥ 1 Dose cohorts. Onset of HZ that occurs during person-time between the first and second RZV doses will be attributed to the RZV or Comparator ≥ 1 Dose cohorts, and not the RZV or Comparator 2-Dose cohorts (see Section 9.2.2). Tofacitinib discontinuation will not censor follow-up for either the primary or the secondary outcome.

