9.7.3.1. RZV 2-Dose Analysis

The RZV 2-dose analysis will be used as the main analysis for assessment of the primary objective for effectiveness. Incidence rates and corresponding 95% confidence intervals for the primary outcome (HZ) will be calculated before and after weighting. All analyses will be performed separately within the UC and RA cohorts. The incidence rate of HZ in the RZV 2-Dose cohort will be compared to the Comparator 2-Dose cohort. Weighted Kaplan-Meier plots will be used to depict the cumulative probability of survival (non-occurrence of the event).

Given the sampling approach that will be utilized in this study (sampling with replacement), we will calculate the number of patients that were selected and included in a study cohort more than once (Section 9.2.3.2.1). If that number exceeds 10% of the study population, then covariance between observations will be taken into account using an appropriate method (eg, generalised estimating equations or robust variance estimators).

The relative hazard will be calculated through weighted Cox regression models with appropriate 95% confidence intervals. Known confounders that are strongly associated with RZV receipt and HZ may also be included in the regression models as well as any variables with an absolute SD >0.1 between weighted exposure cohorts. Additional details on model selection will be detailed in the SAP.

Patients will be further stratified by the following patient groups relative to their matched comparators:

1. Tofacitinib current users at time of receipt of first and second RZV doses;
2. Tofacitinib current users at time of receipt of second RZV dose only.

The first subgroup analysis conducted among patients who receive two doses of RZV and are current users of tofacitinib at the time of receipt of both doses will be the main comparison.

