In addition, using the main study cohorts, Optum will consider applying a more restrictive definition of current tofacitinib exposure (ie, not including the 30-day grace period when identifying current tofacitinib users), and according to cumulative tofacitinib dose. To assess a potential dose-response relationship between tofacitinib exposure and study outcomes, a sensitivity analysis will be performed in which the cohorts are stratified based on tofacitinib dose. Specifically, the daily dose of tofacitinib will be calculated based on dispensings received in the 91 days prior to cohort entry and then the cohorts will be stratified according to high versus low dose of tofacitinib based on the median daily dose. In addition, the cohorts will also be stratified based on cumulative dose of tofacitinib received in the 365 days prior to cohort entry. As patient follow-up will not be censored upon discontinuation of tofacitinib treatment, a sensitivity analysis will be conducted in which patients are stratified based on continued exposure to tofacitinib during follow-up.

As the study period includes time before and during the COVID-19 pandemic, a sensitivity analysis will be conducted stratified by calendar time (cohort entry prior to 20 January 2020 and cohort entry on or after 20 January 2020).

A quantitative bias analysis will also be performed to assess the potential magnitude of bias due to unmeasured confounding, including confounding by incompletely captured or missing covariates (eg, UC/RA severity). A standard epidemiological spreadsheet will be used to assess the robustness of the results in the presence of an unmeasured confounder.³⁴ The results of the main analyses for the association between RZV exposure and the primary and secondary outcomes along with varying magnitudes of the confounder-outcome association and confounder-RZV association will be used to calculate the difference from the observed findings after accounting for the unmeasured confounder. The range of associations to be applied for the confounder-outcome and confounder-RZV associations will be informed by published literature and associations observed for related variables in the current study.

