As patients that have UC and RA may have different clinical characteristics compared to patients that have only one of the two diseases, the number of patients that have both diagnoses will be quantified. Additionally, a sensitivity analysis will be conducted in which the association between RZV exposure and the primary and secondary outcomes is assessed after excluding patients with both UC and RA from the exposure cohorts.

To assess the effect of prior Zostavax vaccination on subsequent RZV effect, an analysis will be performed where the study population is restricted to patients with at least 5 years of enrollment prior to cohort entry. Within this subset, the analysis will be conducted separately among patients with and without Zostavax vaccination during this baseline 5-year period. The effect of prior Zostavax exposure will be informed by the extent to which the estimate of RZV effect differs according to strata of prior Zostavax exposure.

It is possible that the comparator cohorts could include patients previously vaccinated with RZV more than 365 days earlier. To address this potential exposure misclassification, a sensitivity analysis will be performed, for which the study population will be restricted to patients with enrollment that extends back to 20 October 2017 and who do not have any prior administration of RZV during that time. Finally, a sensitivity analysis will be conducted for HZ in which patients are stratified based on their amount of available follow-up time.

Misclassification of disease flares is possible when using claims-based algorithms (for example, patients may change therapy for reasons other than disease flares), leading to over- or under-estimation of the outcome; thus, alternative definitions will be explored and outlined in the SAP as sensitivity analyses. Specifically, sensitivity analysis will explore using a more conservative definition based on only UC-related surgeries or ER and hospitalizations with UC or RA as the primary diagnosis, as well as evaluating more expansive definitions inclusive of other medications of interest, such as biologics or other JAK inhibitor treatments.

Additional sensitivity analysis may be performed if needed.

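### Stratifying whole patients by continued tofacitinib use during follow-up distorts the stratum herpes zoster rates; the analysis by available follow-up has the same fault if observed follow-up is meant

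*Protocol*

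**What the plan says.** Section 9.7.4 plans two sensitivity analyses that group patients by what happens after cohort entry.

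- On tofacitinib: "a sensitivity analysis will be conducted in which patients are stratified based on continued exposure to tofacitinib during follow-up". The stated reason is that follow-up is not censored when tofacitinib stops.
- On duration: "a sensitivity analysis will be conducted for HZ in which patients are stratified based on their amount of available follow-up time".

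Section 9.2.5 fixes how follow-up ends.

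- In the 2-dose analysis, HZ "will be assessed from day 29 after cohort entry until the first occurrence of HZ, disenrollment from the health plan, death", the end of the study period or receipt of RZV. The last of these is defined as "receipt of a third dose for the RZV cohorts or a first dose for the UC comparator and RA comparator cohorts only".
- In the ≥ 1 dose analysis, the RZV rule is "receipt of RZV (patients in the UC comparator and RA comparator cohorts only".
- Section 9.2.5.2 adds: "Tofacitinib discontinuation will not censor follow-up for either the primary or the secondary outcome".

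The effect measure in section 9.7.3.1 is a weighted Cox model: "The relative hazard will be calculated through weighted Cox regression models with appropriate 95% confidence intervals".

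Two other parts of the protocol avoid this kind of classification. Section 9.2.3.2.1.2 builds comparator risk sets to limit the immortal time that arises from classifying patients on later information. The tofacitinib dose strata in section 9.7.4 use only the 91 or 365 days before entry.

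**The concern.** Whether a patient continued tofacitinib is known only when follow-up ends, and HZ is one of the things that ends it. A patient with HZ in month two has had two months in which to stop, and will usually count as a continuer. A patient without HZ must stay on the drug for the whole of follow-up to count as one. Cases therefore collect among continuers. A discontinuer must have been free of HZ up to the stopping date, so that earlier time is immortal and dilutes the stratum's rate.

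The study asks about patients on ongoing tofacitinib, and this analysis is how the protocol examines follow-up after the drug stops. A spurious excess of HZ among continuers could be read as a drug effect, and a spurious difference in vaccine effectiveness (VE) between strata as tofacitinib modifying the vaccine.

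For the second analysis, HZ shortens observed follow-up. If strata are cut on observed time, cases gather in the short stratum, and nobody in the long stratum can have had HZ before the cut.

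**Working it through.** The protocol gives no figure for these analyses, so there is none to reproduce. The check asks what the stated stratification returns when the truth is known.

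**Inputs from the protocol.** Section 9.5 gives a comparator HZ rate of 1.2 per 100 person-years (PY), 2:1 matching, and a VE of 66.7% (hazard ratio, HR, 0.333) as one of its worked values. It considers 2,000 and 4,000 RZV person-years against 1,932 two-dose recipients before eligibility. That is 2,000/1,932 = 1.04 to 4,000/1,932 = 2.07 years each, a rough anchor for follow-up.

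**Assumptions not in the protocol.** Stopping rate *d* of 0.4 to 0.7 per year; follow-up *F* of 1 to 2 years; HZ rare, and its rate the same on and off tofacitinib.

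**Step 1: stratum rates in closed form.** Mean on-drug time per patient is E = (1 − e^(−dF))/d.

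- Continuers hold all on-drug events but only the person-time of patients who never stop. Apparent/true rate = E / (F·e^(−dF)).
- Discontinuers hold only off-drug events but all the person-time of those who stop. Apparent/true rate = (F − E) / (F·(1 − e^(−dF))).

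For d = 0.7 and F = 2: e^(−1.4) = 0.2466 and E = 0.7534/0.7 = 1.076. Continuers: 1.076/(2 × 0.2466) = 2.18. Discontinuers: (2 − 1.076)/(2 × 0.7534) = 0.61.

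| d per year | F, years | Continued | Discontinued | Spurious ratio |
|---|---|---|---|---|
| 0.4 | 1 | 1.23 | 0.53 | 2.3 |
| 0.7 | 1 | 1.45 | 0.56 | 2.6 |
| 0.4 | 2 | 1.53 | 0.57 | 2.7 |
| 0.7 | 2 | 2.18 | 0.61 | 3.6 |

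**Step 2: hazard ratios by simulation.** 2,000,000 patients, 2:1, with true rates 1.20 (comparator) and 0.40 (RZV) per 100 PY and HR 0.333. Assumed: random censoring at 0.3 per year and administrative censoring uniform over 0 to 5.7 years. HZ was independent of tofacitinib status, so a sound analysis returns the same answer in every stratum.

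| Scenario | Comparator rate, continued / discontinued | HR, all patients | HR, continued (VE) | HR, discontinued (VE) |
|---|---|---|---|---|
| A: stopping 0.5 per year, arms alike | 2.22 / 0.75 | 0.340 | 0.339 (66.1%) | 0.344 (65.6%) |
| B: as A, comparators also censored at RZV, 0.2 per year | 1.98 / 0.74 | 0.334 | 0.381 (61.9%) | 0.316 (68.4%) |
| C: stopping 0.6 (comparator) and 0.4 (RZV) per year | 2.46 / 0.77 | 0.328 | 0.271 (72.9%) | 0.302 (69.8%) |

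The rates are wrong in every scenario. The hazard ratios are wrong only when the arms differ, and B and C move continuers in opposite directions. An assumed background of 4.0 per 100 PY gives the same pattern.

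Censoring at discontinuation returned comparator rates of 1.20 to 1.21, RZV rates of 0.40 to 0.41 and HR 0.33 to 0.34. Person-time after discontinuation, counted alone, gave 1.20 to 1.21 and 0.39 to 0.41.

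**Step 3: strata of follow-up time, cut at 1 year (assumed).**

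- *Observed follow-up.* In A the comparator rate is 5.20 below 1 year and 0.72 from 1 year on (5.20/1.20 = 4.3 and 0.72/1.20 = 0.6 times the truth), with the HR about right at 0.34. In B the HR is 0.463 (VE 53.7%) below 1 year and 0.325 (67.5%) from 1 year on.
- *Potential follow-up* (time to censoring, ignoring HZ). Comparator rates are 1.20 to 1.22 and HR 0.32 to 0.37, which is simulation noise around 0.333.

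**The case against.** **Detail left to the analysis plan.** Each analysis gets one sentence, continued exposure is not defined, and the motive is plainly to separate on-drug from off-drug experience. An analysis plan could do that with time-updated person-time. This is fair as to intent. But the sentence already fixes the unit (patients) and a stratifier that arises after entry, and it does not defer to the analysis plan. A plan that follows it inherits the bias.

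**Available may mean potential.** This stands. If the second analysis uses time to data end or disenrolment regardless of HZ, the bias essentially disappears. Section 9.2.5 ends follow-up at HZ, so the observed reading is the natural one, but the wording does not settle it.

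**Effect estimates need not be biased.** A reader might infer that VE within strata is necessarily distorted, and always downward. The documents do not support that. With equal stopping and censoring the hazard ratio is nearly right, and scenario C raises VE. The protocol does build in one asymmetry. Comparators leave at a first RZV dose. RZV patients leave only at a third dose in the 2-dose analysis, and are not censored for RZV at all in the ≥ 1 dose analysis. Its size is not given.

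**Other checks exist.** A reader might also take these two analyses as the only look at off-drug time or at durability. That goes too far. Weighted Kaplan-Meier plots show HZ over time, tofacitinib use during follow-up is described (section 9.3.6.5), and the recent-user cohorts address effects after stopping, though by status at entry.

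**Conclusion.** The point holds for the tofacitinib analysis as written. Under the assumptions of Step 1, the apparent HZ rate is about 1.2 to 2.2 times the truth in continuers and about 0.5 to 0.6 times in discontinuers: a 2.3- to 3.6-fold gap with no tofacitinib effect. The direction follows from the design; the size rests on stopping rates and follow-up that the protocol does not state. Bias in the stratum hazard ratios is conditional on the arms differing in stopping or censoring. That is likely given the RZV censoring rules, but its direction and size cannot be fixed from the documents, and the simulated VE values are illustrations only.

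The follow-up-time analysis is biased if observed follow-up is meant, and essentially not if potential follow-up is meant.

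This does not undermine the main results: the primary and secondary estimates do not use these strata and are unaffected.

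**What to change.** **Tofacitinib analysis.** Replace the patient-level strata in section 9.7.4 with one of these:

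- time-updated tofacitinib status, so that on- and off-treatment person-time and events are counted separately within each cohort; or
- censoring of both cohorts at the end of the on-treatment period already defined in section 9.2.3.1 (days' supply plus 30 days), with inverse-probability-of-censoring weights if stopping is informative.

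**Follow-up analysis.** Either report hazard ratios by time since entry, using everyone still at risk at the start of each interval, or state that strata use potential follow-up, meaning time to data end or disenrolment regardless of HZ.

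**Cost.** A wording change and some extra programming on the same data. The on-treatment analysis will have fewer events, so wider intervals.

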9. RESEARCH METHODS

9.1. Study Design

This is a non-interventional observational cohort study to evaluate the effectiveness and safety of RZV in real-world patients with UC or RA receiving ongoing treatment with tofacitinib. As claims data typically have data lags due to the delay between the occurrence of a health service, claim adjudication, until data availability, adult patients 18 years and older with UC or RA treated with tofacitinib between 20 October 2017 (the date of RZV approval in the US) and 31 July 2023 (or most recent available data at the time the data are extracted) will be identified.

Based on diagnosis of UC or RA and receipt of RZV, patients who are current users of tofacitinib (defined in Section 9.2.3.1) will be classified into the following 8 exposure cohorts, as illustrated by [Figure 1](#).

[figure not shown]
Cohorts for the primary objective (effectiveness):

1. UC RZV 2-Dose: UC patients who receive two doses of RZV;
2. UC Comparator 2-Dose: UC patients who do not receive RZV and are time-matched (within a 4-week window) to patients in the UC RZV 2-Dose cohort;
3. RA RZV 2-Dose: RA patients who receive two doses of RZV;
4. RA Comparator 2-Dose: RA patients who do not receive RZV and are time-matched (within a 4-week window) to patients in the RA RZV 2-Dose cohort;

Cohorts for the secondary objectives (effectiveness and safety):

5. UC RZV ≥ 1 Dose: UC patients who receive at least one dose of RZV;
6. UC Comparator ≥ 1 Dose: UC patients who do not receive RZV and are time-matched (within a 4-week window) to patients in the UC RZV ≥ 1 Dose cohort;
7. RA RZV ≥ 1 Dose: RA patients who receive at least one dose of RZV; and
8. RA Comparator ≥ 1 Dose: RA patients who do not receive RZV and are time-matched (within a 4-week window) to patients in the RA RZV ≥ 1 Dose cohort.

Figure 1. Study Design

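### For herpes zoster, the COVID-19 sensitivity analysis splits patients by entry date while follow-up is uncapped, so the early stratum would probably hold mostly pandemic-era person-time and the contrast is diluted

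*Protocol*

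**What the plan says.** Section 9.7.4 gives the reason for the analysis: "As the study period includes time before and during the COVID-19 pandemic". It then prescribes an analysis "stratified by calendar time (cohort entry prior to 20 January 2020 and cohort entry on or after 20 January 2020"). The heading idea is calendar time; the operational rule is the date of cohort entry.

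Section 9.1 sets the study window at "20 October 2017 (the date of RZV approval in the US) and 31 July 2023", or later if more recent data are available at extraction.

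HZ follow-up is open-ended in both analyses:
- Two-dose analysis (Section 9.2.5.1): "assessed from day 29 after cohort entry until the first occurrence of HZ, disenrollment from the health plan, death, end of the study period". A further vaccine dose also ends it.
- At-least-one-dose analysis (Section 9.2.5.2): "assessed from the day after cohort entry until the first occurrence of HZ, disenrollment from the health plan, death, end of the study period". Among comparators, vaccination also ends it.
- Stopping tofacitinib does not end follow-up: "Tofacitinib discontinuation will not censor follow-up for either the primary or the secondary outcome".

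Flare follow-up is different. Section 9.2.5.2 ends it at the usual censoring events, "receipt of RZV (patients in the UC comparator and RA comparator cohorts only), or 90 days after cohort entry".

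No other analysis in the protocol divides person-time by calendar period. Section 9.7.4 also stratifies HZ by the amount of available follow-up, which is a different axis.

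**The concern.** HZ is identified from a diagnosis code on a claim (Section 9.3.5.1). If the pandemic changed care-seeking or coding for HZ, the change acts on the date of the claim, which may be years after entry. A patient who entered in 2019 counts in the early stratum for every later claim, including those in 2021 and 2022.

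For HZ the comparison is thus a mixed stratum against one that is wholly pandemic. Two readings then become unsafe. Similar estimates would look reassuring although the contrast was weak. Different estimates could reflect time since vaccination as well as era, because only early entrants can have long follow-up.

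**Working it through.** The protocol states no figure for this analysis, so there is nothing to reproduce. The check asks what share of HZ person-time in the early stratum falls on or after 20 January 2020.

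**Inputs from the protocol**
- Entry window before the cut: 20 October 2017 to 20 January 2020 = 822 days (2.25 years).
- Maximum follow-up after the cut: 20 January 2020 to 31 July 2023 = 1,288 days (3.53 years).
- Start of HZ follow-up, *s*: day 29 (two-dose) or day 1 (at least one dose).

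**Assumptions**
- Loss is exponential at rate λ. The protocol gives no forward rate. A rough proxy is prior enrollment in Table 2, which falls between 1 and 5 years from 83.8% to 31.6% (under 60) and from 85.7% to 31.1% (60 and over): ln(83.8/31.6)/4 = 0.24 and ln(85.7/31.1)/4 = 0.25 per year. This looks back in time, so it is indicative only.
- Entry over the 822 days is uniform, linearly rising or linearly falling.

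**Formula.** For a patient entering *x* days before the cut (*x* > *s*):
- person-time before the cut = (e^(−λs) − e^(−λx))/λ
- person-time after the cut = e^(−λx)(1 − e^(−1288λ))/λ

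Both are averaged over *x*. The share is after/(before + after).

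**Worked case, at least one dose, uniform entry, *s* taken as 0**
- No loss: before = 822/2 = 411 days, after = 1,288 days; share = 1288/1699 = 76%.
- λ = 0.25 per year: mean e^(−λx) = (1 − e^(−0.5626))/0.5626 = 0.765. Before = (1 − 0.765)/0.25 = 0.94 years. After = 0.765 × (1 − e^(−0.8816))/0.25 = 1.79 years. Share = 1.79/2.73 = 66%.

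**Share of early-stratum HZ person-time on or after 20 January 2020**

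| Analysis | Entry | No loss | 0.25/year | 0.5/year | Loss rate at which share is 50% |
|---|---|---|---|---|---|
| ≥1 dose | uniform | 76% | 66% | 56% | 0.65 |
| ≥1 dose | rising | 83% | 75% | 67% | 1.12 |
| ≥1 dose | falling | 70% | 57% | 44% | 0.39 |
| 2-dose | uniform | 77% | 67% | 58% | 0.73 |
| 2-dose | rising | 84% | 77% | 70% | 1.33 |
| 2-dose | falling | 71% | 59% | 46% | 0.42 |

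With uniform entry, the share falls below half only when median retention is about one year or less (ln 2/0.65 = 1.07 years; ln 2/0.73 = 0.95 years).

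**Flare, for contrast.** With a 90-day cap and uniform entry, only patients entering in the last 90 days spill over. The share after the cut is 90/(2 × 822) = 5%, and about 11% with rising entry. The entry-date split works there.

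**The case against.** Several points on the other side stand.

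- **Cohort entry is the vaccination date.** Pandemic changes in who was vaccinated, in baseline utilisation covariates and in the 91-day flare exclusion all act at entry. An entry-date split is a legitimate way to examine those, and is a reason to keep it.
- **The contrast is not absent.** The later stratum is entirely pandemic time and the earlier one is mixed, so a pandemic effect would be attenuated rather than hidden.
- **Time-matching protects the hazard ratio.** Comparators enter in the same 4-week windows, so a fall in HZ coding common to both arms largely cancels. Only a differential effect biases the ratio. The protocol also reports incidence rates, however, and these do not have that protection.
- **The percentages rest on assumptions.** Comparators are also censored at RZV receipt, which shortens their follow-up and lowers their share. Section 9.9 acknowledges that plan changes limit follow-up.
- **A person-time split has its own limits.** Before the cut, time since entry reaches at most 2.25 years; after it, up to about 5.8 years (2,110 days). Era and time since vaccination still mix unless this is handled. Earlier entrants who join the later period are those still enrolled and HZ-free, while their weights were estimated at entry.
- **The pre-cut period is sparse.** Suppose all 1,932 two-dose patients in Table 1 were eligible and entered uniformly over the 2,110 days. Then 1,932 × 822/2110 ≈ 753 would enter early. At about 0.9 years each, 1.2 HZ per 100 person-years and an assumed 70% effectiveness, the vaccinated arm would have 753 × 0.9 × 0.012 × 0.3 ≈ 2 events before the UC and RA split.

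These points narrow the concern to HZ and limit what the remedy can deliver. They do not make the entry-date rule isolate HZ experience before the pandemic.

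**Conclusion.** The point holds for HZ only. As written, the rule does not separate HZ experience before the pandemic from HZ experience during it. The early stratum would probably be mostly pandemic person-time: about 57% to 77% at an assumed loss of 0.25 per year, and 70% to 84% with no loss. The exceptions are short retention, or falling uptake with a loss rate above roughly 0.4 per year. These figures describe person-time; that most HZ events would also be pandemic-era is an inference from them.

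A reader might infer that the analysis is void, or that it fails for every outcome. The documents do not support that. Flare stops at 90 days, the HZ contrast is weakened rather than missing, and effects acting at vaccination or baseline are addressed. Nor does the protocol label the early stratum pre-pandemic or say how similar estimates would be interpreted. This is a sensitivity analysis, and the primary estimate is unchanged. The correction is worth making because it is cheap and improves what the analysis can conclude.

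**What to change.** Keep the entry-date split, and for HZ add to Section 9.7.4 an analysis by calendar period of person-time:

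- Earlier period: censor early entrants on 19 January 2020.
- Later period: count person-time and events from 20 January 2020, with earlier entrants contributing by delayed entry. Recheck weighted covariate balance among those still at risk.
- Report HZ rates and hazard ratios for each period.
- Use time since cohort entry as the time scale, so that the arms are compared at the same time since entry, or compare the periods over a common follow-up length. The second option is the more direct protection if effectiveness changes over time, because the time scale alone does not equalise the length of follow-up between periods.

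For flare, the entry-date split can stay as it is; censoring the small amount of follow-up that crosses the cut is optional.

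The cost is a few sentences and a routine person-time split in the planned Cox program. The real downside is few HZ events before the cut, especially within UC and RA separately. That period's estimate will be imprecise, and the report should say so rather than read agreement between periods as proof of no pandemic effect.
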